Subjects will be withdrawn from the study in the event of a medical event or complication (i.e. hospitalization) that may alter the inclusion/exclusion criteria or which limits the patient from safely completing the remainder of the study, or at the discretion of the PI.

Subjects can voluntarily discontinue the study at any time. The participant will then be requested to notify the Principal Investigator, [name], in writing or call at [contact], if assistance is needed in this process. Information collected prior to the study discontinuation by a participant may still be used by the research team.

The researchers reserve the right to discontinue study participation for any individual or for the study as a whole at their discretion.

STU#:00215607

RISKS TO PARTICIPANTS

All testing and training sessions will be under supervision of a trained researcher. Manual assistance or cueing will be provided as necessary for safety and balance. Vital signs will be monitored before and after physical exertion and during activities, as needed. All subjects will be permitted to stop physical activity or rest at any time during the study.

- The risk of falling: This could be caused by loss of control of ambulation by the participant or therapist as well as malfunction of the BiOMOTUM RAAD/SPARK device itself. The risk of falling will be minimized by having experienced SRALAB research personnel conduct the participant training sessions with manual assistance, and as needed overhead attachment with a safety harness and/or gait belt during over-ground gait training.
- Discomfort, skin pressure/friction, bruising, pain, or unusual swelling caused by the exoskeleton which has the potential to lead to skin breakdown or abrasions. This risk will be minimized by a thorough skin check performed by experienced research personnel at each training session. Adjustments to the device fit and additional padding will be assessed to decrease the risk of skin breakdown as well.
- There may also be a risk of skin irritation caused by the adhesives used to secure the sensors, EMG sensors, and IMUs to the participant. This will be reduced by careful monitoring of skin when these devices are utilized.

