10.0 Local Number of Participants

10.1 Local Number of Participants to be Consented:

In total, up to 50 participants may be consented into the study conducted at Gillette, which includes the Exploration phase and Experimental phase.

Up to 20 participants may be consented into the Exploration phase. This is a sample of convenience and is preparatory to Experiments 1 and 2.

Up to 15 participants may be consented into each Experiment (i.e., up to 30 total) to account for possible attrition and incomplete data. This will ensure we reach our recruitment goal of 12 enrolled participants with complete data in each Experiment.

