12.0 Withdrawal of Participants

12.1 Withdrawal Circumstances:

Participants will be withdrawn if they are later identified as not meeting the inclusion criteria (e.g., identified as eligible in error), if they miss more than 3 research visits in a given Experiment, or if they decide to stop participating in the study.

12.2 Withdrawal Procedures:

MEDICAL PROTOCOL (HRP-590)

PROTOCOL TITLE: Development of a robotic ankle assist device to improve mobility in individuals with movement disorders

VERSION DATE: 11/09/2022

If a participant consents to the study but elects to stop participating after data collection has started, any data that was collected will be retained unless the participant asks otherwise.

Participants must alert the study team in writing of their request to be withdrawn from the study.

12.3 Termination Procedures:

Data collected and completed up to the point of withdrawal or termination will still be included in the study unless the participant asks otherwise.

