15.0 Statistical Considerations

15.1 Data Analysis Plan:

Data will be collected and analyzed by Gillette study team members and collaborators.

Exploration:

As described below, the Exploration phase is a sample of convenience, and these activities are preparatory to the Experimental phase.

Experiments 1 and 2:

For Experiments 1 and 2, power analyses were used to determine estimated sample sizes. Statistical procedures include Repeated Measures ANOVA (RM-ANOVA) and generalized linear models. Participants in each Experiment will be age-, GMFCS-, and sex-matched as appropriate to control for known and unknown covariates. Participant demographics and baseline characteristics will also be analyzed.

15.2 Power Analysis:

Exploration:

No power analysis was done for the Exploration phase; this is a sample of convenience.

Experiment 1:

The sample size for the primary outcome measure in Experiment 1, mean stance phase plantar-flexor activity, was determined for the Repeated Measures ANOVA (RM-ANOVA). We set the Type II error rate (beta) at 0.2, and therefore the power level at 0.8 and alpha at 0.05. Sample size was determined based on the difference in soleus activity (45 ± 35%) from our collaborators preliminary ABS resistance validation study. We found that a subject sample size of n = 10 will

MEDICAL PROTOCOL (HRP-590)

PROTOCOL TITLE: Development of a robotic ankle assist device to improve mobility in individuals with movement disorders

VERSION DATE: 11/09/2022

allow us to find significance. We will enroll and collect complete data for 12 participants to provide an adequate sample for our investigation into participant characteristics that will be correlated with outcomes.

Experiment 2:

The sample size for the primary outcome measures in Experiment 2 was determined for the RM-ANOVA using our preliminary over-ground RAAD assistance training study (speed: $24\pm10\%$; normality of soleus profile: $39\pm20\%$; see section 2.2 Preliminary Data). We found that a sample size of $n = 5$ will allow us to find statistical significance for the assistance training protocol. We will enroll 12 participants to provide an adequate sample for our investigation into participant characteristics (i.e., covariates) that will be correlated with outcomes.

15.3 Statistical Analysis:

Exploration:

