Chief Science Officer

NCT04516343

**Title: Evaluation of the Safety and Efficacy of a Lower Extremity
BiOMOTUM Exoskeleton in the Pediatric Population with
Cerebral Palsy**

2/6/2025

Statistical Analysis Plan

Gait Training with RAAD assistance statistical analysis:

The RAAD assistance training protocol took place under the supervision of [name] at Gillette Children's Specialty Healthcare. We completed the protocol with 12 participants for this arm of the study. Participants completed a pre-training assessment and then 12 sessions (roughly 3 per week for 4 weeks) of RAAD assistance over-ground walking training. Walking speed was measured using a gait timer; the distance in meters was divided by the completion time in seconds. Walking distance was measured using a distance wheel measuring tool. To calculate the metabolic cost of transport, the standing baseline metabolic rate for each participant and each trial was subtracted from their walking metabolic rate to estimate the net metabolic rate of walking. Next, we normalized the net metabolic rate of walking by each participant's body mass and walking speed to calculate the metabolic cost of transport. Outcomes were assessed during walking without the RAAD before and within one week after the last training session. We checked outcome measures data for normality using a Shapiro-Wilks test. For data that were normally distributed, we tested for statistical differences using paired Student's T-tests (two tailed, alpha set to 0.05).

Gait Training with RAAD resistance statistical analysis:

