The RAAD resistance training protocol took place under the supervision of [name] at the Shirly Ryan Ability Lab. We completed the protocol with 16 participants for this arm of the study (Table 5). Participants completed a pre-training assessment and then 12 sessions (roughly 3 per week for 4 weeks) of RAAD resistance treadmill walking training with plantar pressure biofeedback. The resistance level was gradually increased to ensure progression. Walking speed was measured using a gait timer; the distance in meters was divided by the completion time in seconds. Walking distance was measured using a distance wheel measuring tool. To calculate the metabolic cost of transport, the standing baseline metabolic rate for each participant and each trial was subtracted from their walking metabolic rate to estimate the net metabolic rate of walking. Next, we normalized the net metabolic rate of walking by each participant's body mass and walking speed to calculate the metabolic cost of transport. Outcomes were assessed without the RAAD before and within one week after the final training session. We checked outcome measures data for normality using a Shapiro-Wilks test. For data that were normally distributed, we tested for statistical differences using paired Student's T-tests (two tailed, alpha set to 0.05).

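### The speed analysis is planned on completers only: any child who begins training and is withdrawn before the post-test would be left out, and the number who began is not stated

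*Protocol*

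**What the plan says.** **Withdrawal.** Gillette protocol, 12.1, withdraws participants found ineligible, and also "if they miss more than 3 research visits in a given Experiment, or if they decide to stop participating in the study". Section 12.3 then states: "Data collected and completed up to the point of withdrawal or termination will still be included in the study", unless the participant asks otherwise. The Shirley Ryan protocol (Withdrawal of Participants) reads "Subjects will be withdrawn from the study in the event of a medical event or complication (i.e. hospitalization"). This is limited to events that bear on eligibility or prevent safe completion, and the principal investigator may also withdraw a child at discretion. Data gathered before discontinuation may be used.

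**Timing of the post-test.** Gillette 4.1 and 5.2 place the follow-up visits, at 3 days and 3 weeks, after all training visits are complete. Shirley Ryan (Outcome Measures) places them 2 to 7 days after the intervention, with 12 sessions given in brackets, and 3 weeks after the final session. Neither protocol describes a walk test for a child who stops early.

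**Numbers.** Gillette 10.1 allows up to 15 consents per experiment to cover attrition and incomplete data: "This will ensure we reach our recruitment goal of 12 enrolled participants with complete data in each Experiment". Shirley Ryan (Recruitment Methods) adds 2 to 3 subjects to cover withdrawal.

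**Analysis.** The SAP says of assistance: "We completed the protocol with 12 participants for this arm of the study". Of resistance it says: "We completed the protocol with 16 participants for this arm of the study". Normally distributed outcomes get a paired t-test, "two tailed, alpha set to 0.05". The SAP names no analysis set, gives no rule for a missing post-training value, and states no number who began or stopped.

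**The concern.** A paired pre/post test needs both values from the same child. If the second value is collected only after training is finished, and a child who falls behind is withdrawn, then following the plan as written selects the analysed children on completion.

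Completion may be related to outcome. A child who tolerates the device poorly, tires, or sees no gain is a plausible candidate to miss visits or stop.

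Self-selected speed is the Shirley Ryan efficacy primary, and preferred speed is a Gillette Experiment 2 primary. The SAP has no untreated comparison, so the within-child change is the whole efficacy result. With 12 and 16 children, a few omitted stoppers can move the mean noticeably. At stake is whether the result can be read as the change to expect in children who start training, or only in those who finish.

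**Working it through.** **1. The plan's own figures (Gillette 10.1 and 15.2).** Inputs: speed change 24 ± 10%, soleus-profile change 39 ± 20%, stated n = 5. Section 15.2 says, under Experiment 1, "We set the Type II error rate (beta) at 0.2, and therefore the power level at 0.8 and alpha at 0.05"; I assume this carries over to Experiment 2. I treat the SDs as SDs of the change and use exact paired t power (noncentral t, df = n − 1, noncentrality d√n, two-sided 0.05).

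- Speed: d = 24/10 = 2.40; n = 4 gives power 0.877.
- Soleus: d = 39/20 = 1.95; n = 4 gives 0.736, n = 5 gives 0.896.
- The larger requirement is 5, which matches the plan.
- Attrition allowance: 12/(1 − 0.20) = 15, which matches 10.1.

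So no planning figure is wrong here. The question is who enters the test.

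**2. Who can contribute to the paired test.**

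| Child | Baseline | Post-training value under the schedule | In the paired test |
|---|---|---|---|
| Finishes training | yes | yes | yes |
| Begins, withdrawn before the post-test | yes | none described | no |
| Consents, never trains | possibly | no | no, and not a starter |

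The second row is the point at issue.

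**3. Size for the assistance arm.** Let N completers have mean m and let k stoppers have mean change g.

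- Mean over starters = (N·m + k·g)/(N + k)
- Excess of the completer mean = k(m − g)/(N + k)

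Take N = 12, m = 24, SD = 10 (planning values) and assume g = 0 for each stopper. The completer sum is 12 × 24 = 288 and the sum of squares is 11 × 100 + 12 × 576 = 8012.

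For k = 3:
- mean = 288/15 = 19.2
- SS = 8012 − 15 × 19.2² = 2482.4
- SD = √(2482.4/14) = 13.3
- t = 19.2/(13.3/√15) ≈ 5.6, p < 0.001
- 24/19.2 = 1.25

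| Stoppers k | Mean over starters | Factor 12/(12 + k) | p |
|---|---|---|---|
| 0 | 24.0% | 1.00 | < 0.001 |
| 1 | 22.2% | 0.92 | < 0.001 |
| 2 | 20.6% | 0.86 | < 0.001 |
| 3 | 19.2% | 0.80 | < 0.001 |

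Sensitivity to g at k = 3: the excess is 0.2 × (24 − g) percentage points. That is 4.8 at g = 0, 2.4 at g = 12 and 0 at g = 24. It exceeds 4.8 if stoppers got slower.

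**4. Resistance arm.** The number who began is not given, and no planning speed effect is stated for resistance. Under zero change in stoppers the factor is 16/(16 + k): 0.94 for one, 0.89 for two, 0.80 for four. These illustrate the formula and do not estimate what happened.

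**The case against.** The strongest reply is that this builds on silence. No passage says that any child began and stopped, and no passage says in terms that assessment ends at withdrawal; that is inferred from the visit schedule and the absence of any other provision. Both points stand, so the claim must be conditional.

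The 1.25 is also open to attack, and fairly. Fifteen is a cap on consents, and Gillette 8.3 has children sign a consent form at a screening visit whether or not they are enrolled. The allowance covers incomplete data as well as attrition. Three stoppers among 15 starters is therefore an upper case, and zero gain is a further assumption. A child who leaves the study altogether cannot be assessed under any plan. The p-value does not move under the planning effect.

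Three stronger readings are tempting, and the documents do not support them.

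- A reader might infer that the SAP breaks a promise in Gillette 12.3. That sentence sits beside the retention wording of 12.2, carries an opt-out, covers Gillette only, and promises no place in the speed test. Section 10.1 openly aims for 12 with complete data.
- A reader might infer that the two arms contain differently selected children because only Gillette lists missed visits as a ground for withdrawal. Both sites state a limit of three missed, Shirley Ryan adds investigator discretion, and the SAP makes no comparison between arms.
- A reader might take the gap between 16 completers and the planned Shirley Ryan number (up to 30 in its own protocol, 24 in Gillette 23.1) as dropout. It may equally be under-recruitment.

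None of this removes the gap: as planned, the test selects on completion, and the SAP gives the reader no way to tell whether that mattered.

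**Conclusion.** The point holds in conditional form. Withdrawal for missed visits (Gillette), a post-test tied to finishing training (both sites) and a paired test on completers (SAP) together mean that any child who began and was withdrawn before the post-test would not be in the speed result. That result would describe completers.

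In the assistance arm the overstatement runs from nil to 1.25 times the starter mean (24% against 19.2%). The upper end assumes that all 15 places were starters, that 3 stopped with zero change, and that completers match the planning effect. In the resistance arm it cannot be bounded from the documents. What is affected is the size of the estimate and the population it describes, not statistical significance under the planning effect. The safety count is not in question.

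The boundary of a completer is itself unclear. Gillette 4.1 has 12 visits with at most 3 missed, Gillette 5.2 has 8 to 12, Shirley Ryan allows a minimum of 9, and the SAP describes 12. These passages must be reconciled.

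**What to change.** **Protocols (both withdrawal sections).** Distinguish stopping training from leaving the study. Invite a child who stops training or misses visits to the already planned post-training and 3-week assessments, unless the family declines or the investigator judges assessment unsafe.

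**SAP.**
- Define the analysis set as every child with a baseline who began at least one training session, and use any post-training value obtained.
- Report, for each arm, the numbers who began, stopped and were assessed.
- Label the result on 12 and 16 children a completer analysis.
- Add a sensitivity analysis for starters without a post-training value, for example with zero change.
- State what counts as completing, once the session counts are reconciled.

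The SAP is dated 2/6/2025 and written in the past tense. If the data are closed, only the SAP changes apply.

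**Cost.** Up to two already planned visits for each of the few children who stop, some SAP wording and one extra analysis. The Shirley Ryan Data Safety and Monitoring Plan already has a Safety Officer at each site review the numbers withdrawn and completing each phase, so the counts should largely be to hand. The estimate may come out less favourable.

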13.0 Risks to Participants

13.1 Foreseeable Risks:

The potential minimal risks associated with this study are as follows:

First, is the risk of falling during ambulatory activities performed during this protocol but this is no greater than during normal daily life. Additionally, this risk will be minimized by supervision from a licensed PT and the use of a safety harness and/or walker for unstable participants.

Second, is the risk of fatigue, shortness of breath, or muscle soreness during or after the research visits. It is expected that when these symptoms occur, they will be minor and brief. If a participant experiences excessive shortness of breath or fatigue, they will be allowed to stop and given adequate rest before continuing. Should the participant experience any muscle soreness, light stretching, and hot/cold therapy will be recommended to reduce soreness. If these approaches do not alleviate the soreness, we will advise the use of OTC pain relievers (e.g., aspirin, acetaminophen, ibuprofen), unless contraindicated. As previously mentioned, a licensed PT will be present at each research visit.

Third, there is a risk of stumbling or falling while walking with the ABS. The amount of ankle assistance/resistance is not designed or able to completely overpower the user. As previously mentioned, several safety precautions are implemented to ensure participant safety, including mechanical “stops” to prevent hyperextension of joints, an emergency stop button that shuts off power to the device, and embedded software mechanisms that shut off power if the user were to fall. Lastly, a licensed PT will be present at each research visit.

Fourth, there is a small risk of loss of confidentiality as part of participating in research. Study team members are trained on appropriate data use and storage, and every reasonable effort is made to minimize risk associated with loss of privacy and confidentiality.

13.2 Reproduction Risks:

MEDICAL PROTOCOL (HRP-590)

PROTOCOL TITLE: Development of a robotic ankle assist device to improve mobility in individuals with movement disorders

VERSION DATE: 11/09/2022

N/A

13.3 Risks to Others:

N/A

14.0 Potential Benefits to Participants

14.1 Potential Benefits:

Potential benefits for this study include determining if wearable ankle assistance or resistance are viable treatment strategies for our participants, which can be used to guide future treatments and therapy and possible improvement in mobility.

15.0 Statistical Considerations

15.1 Data Analysis Plan:

Data will be collected and analyzed by Gillette study team members and collaborators.

Exploration:

As described below, the Exploration phase is a sample of convenience, and these activities are preparatory to the Experimental phase.

Experiments 1 and 2:

For Experiments 1 and 2, power analyses were used to determine estimated sample sizes. Statistical procedures include Repeated Measures ANOVA (RM-ANOVA) and generalized linear models. Participants in each Experiment will be age-, GMFCS-, and sex-matched as appropriate to control for known and unknown covariates. Participant demographics and baseline characteristics will also be analyzed.

15.2 Power Analysis:

Exploration:

No power analysis was done for the Exploration phase; this is a sample of convenience.

Experiment 1:

The sample size for the primary outcome measure in Experiment 1, mean stance phase plantar-flexor activity, was determined for the Repeated Measures ANOVA (RM-ANOVA). We set the Type II error rate (beta) at 0.2, and therefore the power level at 0.8 and alpha at 0.05. Sample size was determined based on the difference in soleus activity (45 ± 35%) from our collaborators preliminary ABS resistance validation study. We found that a subject sample size of n = 10 will

MEDICAL PROTOCOL (HRP-590)

PROTOCOL TITLE: Development of a robotic ankle assist device to improve mobility in individuals with movement disorders

VERSION DATE: 11/09/2022

allow us to find significance. We will enroll and collect complete data for 12 participants to provide an adequate sample for our investigation into participant characteristics that will be correlated with outcomes.

Experiment 2:

The sample size for the primary outcome measures in Experiment 2 was determined for the RM-ANOVA using our preliminary over-ground RAAD assistance training study (speed: $24\pm10\%$; normality of soleus profile: $39\pm20\%$; see section 2.2 Preliminary Data). We found that a sample size of $n = 5$ will allow us to find statistical significance for the assistance training protocol. We will enroll 12 participants to provide an adequate sample for our investigation into participant characteristics (i.e., covariates) that will be correlated with outcomes.

15.3 Statistical Analysis:

Exploration:

16.0 Health Information and Privacy Compliance

16.1 Select which of the following is applicable to your research:

- My research does not require access to individual health information and therefore assert HIPAA does not apply.
- I am requesting that all research participants sign a HIPCO approved HIPAA Disclosure Authorization to participate in the research. The stand alone HIPAA Authorization will be used.**
- I am requesting the IRB to approve a Waiver or an alteration of research participant authorization to participate in the research.

Appropriate Use for Research: N/A

- An external IRB (e.g. Advarra) is reviewing and we are requesting use of the authorization language embedded in the template consent form in lieu of the U of M stand-alone HIPAA Authorization. Note: External IRB must be serving as the privacy board for this option.

16.2 Identify the source of Private Health Information you will be using for your research (Check all that apply)

- I will use the Informatics Consulting Services (ICS) available through CTSI (also referred to as the University's Information Exchange (IE) or data shelter) to pull records for me
- I will collect information directly from research participants.**
- I will use University services to access and retrieve records from the Bone Marrow Transplant (BMPT) database, also known as the HSCT (Hematopoietic Stem Cell Transplant) database.
- I will pull records directly from EPIC.
- I will retrieve record directly from axiUm / MiPACS
- I will receive data from the Center for Medicare/Medicaid Services
- I will receive a limited data set from another institution

MEDICAL PROTOCOL (HRP-590)

PROTOCOL TITLE: Development of a robotic ankle assist device to improve mobility in individuals with movement disorders

VERSION DATE: 11/09/2022

Other. Describe: Information will be collected from the Gillette medical record. LAR will sign a HIPAA Authorization as part of this research allowing study team members to access the participant's medical record.

16.3 Explain how you will ensure that only records of patients who have agreed to have their information used for research will be reviewed.

Only the records of participants that have signed the consent form and HIPAA Authorization will be used for data collection and analysis associated with this research. Oversight of this will primarily be done by the site PI (PI [name]). All study team members will have been appropriately trained on HIPAA practices, obtaining authorization, and any related requirements prior to any participant interaction and research activities.

16.4 Approximate number of records required for review:

N/A

16.5 Please describe how you will communicate with research participants during the course of this research. Check all applicable boxes

This research involves record review only. There will be no communication with research participants.

Communication with research participants will take place in the course of treatment, through MyChart, or other similar forms of communication used with patients receiving treatment.

Communication with research participants will take place outside of treatment settings.

Communication with potential and enrolled participants will be done via phone, email, and/or in-person. This will be outside the context of standard of care treatment, and may include inquiring about study interest, reminding of upcoming appointments, or contacting for follow-up after participation.

